Enrollment of subjects within the original study framework was put on hold beginning on March 16, 2020 due to the necessary hospital response to prevent further spread of COVID-19 and to maximize resources to treat hospitalized patients. Adding a second control group where all variables except for biologic and survey data will allow comparison of three different care conditions, intervention plus usual care, usual care only and usual care only during a pandemic. Usual care in terms of study visit timing, number, and length may be different than pre-pandemic care paradigms due to staff redeployment and restructuring are care areas to support care during a disaster.

3. Study Procedures

- a. Study design, including the sequence and timing of study procedures (distinguish research procedures from those that are part of routine care).

This pilot study uses a randomized parallel group design to determine the difference in the expression of pro- and anti-inflammatory cytokines in response to this specific exercise intervention plus usual care versus usual care only. Patients will be enrolled on day 3 of illness and data will be collected for seven consecutive days. We seek to enroll a convenience sample of up to 100 consecutive patients with supratentorial sICH and acute ischemic stroke admitted to the Johns Hopkins Hospital Neurosciences Critical Care Unit (NCCU). Patients will be screened within 24-48 hours of arrival for eligibility according to the inclusion and exclusion criteria listed below. Informed consent will be obtained from the patient or legally authorized representative (LAR). The consenting process will be performed remotely via videoconference when possible.

Patients will be randomly assigned to the intervention plus usual care or usual care only group using a standard randomization schema generated by STATA 14.0 (College Station, Texas). The AIS and sICH cohorts will have separate randomization schemas.

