arterial line is not available the non-invasive cuff will be cycled every 5 minutes. Continuous vital signs will be extracted from the Sickbay software application, which collects physiologic data on all NCCU (see IRB00132987 Multimodality Neuromonitoring in the Neurocritical Care Unit). A clinician will observe the patient at all times during the session for signs of pain and discomfort and will administer the behavioral or visual analog pain scale every 5 minutes during the session depending on the patient's level of consciousness. Patient tolerance will be defined as the absence of the following: decline in neurological examination; sustained change in intracranial pressure, blood pressure, heart rate or oxygen saturation outside of prescribed goals per established patient specific plan of care; an increase in pain as measured by the behavioral pain scale or numeric pain rating scale not easily ameliorated by position change by the clinician; and accidental tube/device/catheter removal.^{22,34} Manual muscle strength testing using the Medical Research Council Sum Score will be performed by a clinician before the first session on days three and seven for patients in the control group. General strength will be assessed using a hand-held dynamometer for patients able to follow simple commands before the first session on days three and seven for patients in the control group. Other relevant covariates will be extracted from the medical record such as delirium screening, hospital acquired infections, volume of hematoma and cerebral edema on routine CT scans and body temperature.

The second control group, retrospective observational cohort, will consist of ischemic and hemorrhagic stroke patients admitted to the NCCU on the Johns Hopkins Hospital and Johns Hopkins Bayview campuses from March 16, 2020 through the end of the prohibition of tier II and III studies declared by the Johns Hopkins University Institutional Review Board. All data collection will be accomplished through retrospective chart abstraction. Face-to-face contact will not be required. The same clinical variables will be collected for this cohort to the extent that they are recorded in the medical record from admission to 90 days after the initial ischemic or hemorrhagic stroke.

The following samples will be obtained for the intervention + usual care group and the control group, usual care only:

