Usual care in the NCCU consists of evaluation and treatment by physical and occupational therapists assigned to the neurosciences service when an order for evaluation and treatment is entered by medical providers. Patients may be seen up to 5 times per week depending on their level of participation and intensity of therapy required, however many patients with sICH particularly those in coma are treated by therapists 2 times per week. Nursing staff in the NCCU provide passive range of motion and progressive a patient's mobility from supine to upright positioning, sitting at the side of bed, transferring to chair, lift assisted transfer to chair and ambulation as the patient's condition allows. All usual care activities will be recorded by the study team via extraction from the medical record. Usual care during the pandemic is similar to the care described above however, due to resource constraints it is possible that care focused on mobility and recovery was reprioritized in order to provide acute and intensive care for other patients.

Table 1. Study Activities Schedule for the intervention and prospective control group

	Admission day 1-2	Study day 1 = hospital day 3	Study day 2 = hospital day 4	Study day 3 = hospital day 5	Study day 4 = hospital day 6	Study day 5 = hospital day 7	Study day 6 = hospital day 8	Study day 7 = hospital day 9	Day of ICU transfer	30 days after hemorrhage (-10, +30 days)
Screening, Inclusion/Exclusion, Consent	X									
Intervention and monitoring										
Cycle ergometry 20 minute sessions (twice each study day)		XX								
Vital signs (BP, HR, RR, SpO ² , ICP)		X	X	X	X	X	X	X		
Pain scores		X	X	X	X	X	X	X		
Physiologic outcomes for the intervention and control groups										
Blood draw (IL1- β , IL-6, TNF- α , IL-10, CRP, BDNF)		X		X				X		
Saliva sample for cortisol		X		X				X		
CSF sampling, if a external ventricular		X		X				X		

drain is in place										
Outcome measures										
Medical Research Council Sum Score (strength testing) ²¹		X		X				X	X	X
Grip strength		X		X				X	X	X
Modified Rankin scale score	X								X	X
Barthel Index ¹²									X	X
Sunnybrook Neglect Assessment Procedure (SNAP) ³¹		X							X This battery will only be completed if the patient was found to have neglect on the initial assessment.	X This battery will only be completed if the patient was found to have neglect on the initial assessment.
Questionnaires										

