Promis Global Measure of Health v1.2 to patient or legally authorized representative (LAR)		X								
Stroke										X

Impact Survey to patient or LOR										
---------------------------------	--	--	--	--	--	--	--	--	--	--

b. Study duration and number of study visits required of research participants.

The study will enroll patients for approximately two years. Each patient will receive study interventions or procedures depending on group assignment for 7 days, assessment of motor function and physical/cognitive functioning on transfer from the NCCU or 1 day after the last study day if the patient completed study activities outside of the NCCU and 30 days (-10 days, +30 days) after occurrence of sICH. We will allow a 30 day time period in which to contact the patient if they are not able to be contacted on the 30th day for a total study period of 60 days. If a patient is seen in clinic prior to the 30 day period after the hemorrhage, follow-up assessments will be performed at that time. The stroke service currently collects a modified Rankin score for all ischemic and hemorrhagic stroke patients at 90 days via phone as a standard of care. We will record this value for all patients in this study. If a patient is not scheduled for an in-person visit after discharge, only the 90 day modified Rankin scale will be collected as an outcome measure.

c. Blinding, including justification for blinding or not blinding the trial, if applicable.

This pilot trial cannot be blinded because of the use of the supine cycle ergometer which is a large piece of equipment introduced into the patients' rooms in the intervention group twice per day during the initial study period, however outcome measures at NCCU transfer and 30 days will be obtained by a study team member blinded to the participant's group assignment.

d. Justification of why participants will not receive routine care or will have current therapy stopped.

Current therapy will not be stopped. Participants will receive the study intervention in addition to usual care.

e. Justification for inclusion of a placebo or non-treatment group.

In order to detect a signal of cytokine modulation with the intervention regimen of supine cycle ergometry, a control group not receiving the intensive intervention regimen is necessary for comparison.

f. Definition of treatment failure or participant removal criteria.

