Aim 2: To determine the effects of twice-daily, lower extremity CE of 20 minutes duration plus usual care compared to usual care alone and a third retrospective cohort of patients receiving usual care during the COVID-19 pandemic on, the immediate and sustained physical impairment and disability scores at NCCU discharge and 30 days after hemorrhage.

Data from this aim will be analyzed in the same fashion as described above.

Hypothesis: The CE group will demonstrate decreases in 90-day modified Rankin Scale score, increases in the Medical Research Council sum score (muscle strength) and grip strength, less delirium positive days and hospital acquired infections.

d. Early stopping rules.

If a patient meets the following stopping criteria on >2 consecutive sessions the patient will be withdrawn from the study: change in neurological examination, sustained change in intracranial pressure, blood pressure, heart rate, or oxygen saturation that is outside of provider-prescribed range or significant pain exacerbated by mobilization.

6. Risks

a. Medical risks, listing all procedures, their major and minor risks and expected frequency.

The risks of this study are designed to be minimal. Potential risks to the participant include the following: hemodynamic instability, increased intracranial pressure, skin breakdown associated with the supine cycle ergometer, pain, muscle spasm and musculoskeletal injury.

b. Steps taken to minimize the risks.

Patients are continuously monitored on a cardiorespiratory monitor with oxygen saturation, heart rate, intracranial pressure (when applicable) and blood pressure, measured by arterial catheter or non-invasive cuff. Blood pressure, heart rate, oxygen saturation, respiratory rate and intracranial pressure will be measured and recorded continuously using the Medical Informatics, Sickbay software application currently installed in the NCCU and collecting data from all cardiorespiratory monitors. Pain will be measured and documented every 5 minutes visual analog scale or behavioral pain scale in patients unable to report pain level.

The NCCU is staffed 24 hours per day by a dedicated team of Neuro Intensivists, fellows and resident physicians assigned exclusively to the unit who can respond immediately to physiologic changes or adverse events when notified. A chain of command is followed when a primary provider is not available to respond due to other emergent patient care duties.

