Administration of cycle ergometry will be performed by the Principal Investigator or trained registered nurses (RN) who currently perform this therapy in the NCCU and have been trained in current personal protective equipment standards in the setting of the novel Coronavirus pandemic. These clinicians are in possession of reusable face shields and masks as part of their routine work. All clinicians performing the intervention will have documented competency using a standardized competency checklist including physiologic monitoring considerations, positioning and alignment of the patient in the cycle ergometer and considerations for the management of lines and tubes to mitigate risk of dislodgement. The applicant will observe the application and performance of CE performed by unit RNs during 10% of sessions to assure correct procedure. All procedures for applying the CE to the patient will be explained to the patient or family member(s) in attendance. A physical therapist is part of our study team and will provide consultation as needed regarding cycle ergometry. Standard disinfection of the ergometer, inclusive of current guidelines for prevention of Coronavirus transmission, will be performed at the conclusion of each session by the study team.

A recent prospective safety and feasibility study of supine cycle ergometry in critically ill patients found only one adverse event in 541 sessions (181 patients), dislodgement of a radial arterial line. Another recent prospective study of 20 patients in an NCCU with intracranial pressure monitoring, 3 of which had a diagnosis of sICH, found no significant increases in intracranial pressure. Since, cycle ergometry is currently available in the NCCU, we performed an internal retrospective evaluation of 23 patients with an

intraventricular catheter (intracranial pressure monitor) over 32 sessions receiving supine lower extremity cycle ergometry. This evaluation revealed no peripheral oxygen desaturation, hemodynamic instability and no increases in intracranial pressure requiring an end to the session or further treatment.

Procurement of blood specimens will occur in tandem with standard of care blood draws (phlebotomy or arterial line) when possible and will be drawn by the applicant or the registered nurse caring for the patient. CSF specimens will be obtained using a protocol developed by the sponsor for a previous clinical trial requiring CSF sampling from an external ventricular drain.

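### Aim 2's three-group comparison is not supported for MRC, grip, Barthel and mRS at NCCU discharge and 30 days, and its two usual-care conditions overlap in time

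*Combined protocol and SAP*

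**What the plan says.** Aim 2 (Study Statistics, part c; also secondary objective (i)) compares cycling plus usual care, usual care alone and a retrospective pandemic cohort on "the immediate and sustained physical impairment and disability scores at NCCU discharge and 30 days after hemorrhage". Its hypothesis names the 90-day mRS, MRC sum score, grip strength, delirium positive days and hospital acquired infections.

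For the randomised arms, Table 1 schedules MRC, grip, Barthel and mRS at ICU transfer and at 30 days. The table's title limits it to the intervention and prospective control groups. Section 3c has a blinded team member obtain the outcomes at those two times.

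For the pandemic cohort, section 3a states: "All data collection will be accomplished through retrospective chart abstraction. Face-to-face contact will not be required". It continues: "The same clinical variables will be collected for this cohort to the extent that they are recorded in the medical record", over a window from admission to 90 days. The Background section is more ambitious: "Adding a second control group where all variables except for biologic and survey data will allow comparison of three different care conditions". I read this as all variables being collected apart from biologic and survey data. Table 1 lists MRC, grip, Barthel and mRS as outcome measures, apart from its questionnaires, so that exclusion does not remove them.

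On pandemic care, section 3a describes usual care as similar to before but adds that "it is possible that care focused on mobility and recovery was reprioritized". On routine outcomes, section 3b says: "The stroke service currently collects a modified Rankin score for all ischemic and hemorrhagic stroke patients at 90 days via phone".

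On timing, enrolment was put on hold from March 16, 2020. The pandemic cohort runs from that date until the institution's prohibition on tier II and III studies ends. Section 6b says the staff who deliver cycling "have been trained in current personal protective equipment standards in the setting of the novel Coronavirus pandemic".

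**The concern.** There are two separate problems.

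The first is the source of the outcomes. A score from a scheduled, blinded assessment would be compared with a score that someone happened to enter in a chart. No section says that MRC, grip, Barthel, or mRS at discharge or 30 days is charted in routine care. If strength and function are charted mainly when a patient is seen for mobility care (a reasonable inference, not something the plan states), the charted subset is selected by the very care that is being compared. A difference between groups could then reflect who was charted or how the score was taken.

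The second is the period. The plan sets out a "comparison of three different care conditions, intervention plus usual care, usual care only and usual care only during a pandemic". The pandemic cohort closes when the research prohibition ends, not when the pandemic does. Controls enrolled after the restart are therefore treated during the pandemic too, and nothing in the plan separates them from controls enrolled before the hold.

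The analysis does not deal with either problem. Aim 2 is to be analysed like Aim 1, with a two-sample t-test, or ANCOVA if baseline differs. The plan gives no three-group model, no missing-data method, no period split and no sample size for the third cohort.

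**Working it through.** **Planning figure, used only for scale.** Study Statistics, part c, gives an effect size of 0.28, 80% power, α of 0.05 and a full-trial total of 400. With a two-sided test, n per arm = 2 × (1.960 + 0.842)² / 0.28² = 200.2, rounded up to 201, so 402 in total. The t-based version gives 404, and power at 200 per arm is 0.7996. The stated 400 is reproduced, and 9% of it is 36. None of this is disputed. The 0.28 comes from a study of cytokine change, so it is a yardstick here and not a planned effect on strength or disability.

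**Source of each Aim 2 outcome.**

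| Outcome | Randomised arms | Pandemic cohort |
|---|---|---|
| MRC, grip, Barthel, mRS at transfer and 30 days | Table 1 schedule, blinded assessor (30 days: if seen in person) | Chart, if recorded |
| 90-day mRS | Stroke service's routine call | Same call, within the 90-day abstraction window |
| Delirium, hospital acquired infections | Medical record | Medical record |
| Discharge location | Source not stated; presumably the record | Presumably the record |

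Only the first row has a different source by group.

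**Selective charting.** Let a share c of the pandemic cohort have a charted score, and let charted and uncharted patients differ in mean by D SD. The whole-cohort mean is c × (charted mean) + (1 − c) × (uncharted mean). The charted mean therefore departs from it by (1 − c) × D. The documents give neither c nor D, so both are assumed:

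| c | D = 0.28 | D = 0.5 | D = 1.0 |
|---|---|---|---|
| 0.9 | 0.03 | 0.05 | 0.10 |
| 0.7 | 0.08 | 0.15 | 0.30 |
| 0.5 | 0.14 | 0.25 | 0.50 |
| 0.3 | 0.20 | 0.35 | 0.70 |

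With half charted, the shift reaches 0.28 SD when D = 0.56 (0.5 × 0.56). For comparison, the 95% half-width for 20 versus 20 is 1.96 × √(2/20) = 0.62 SD. Most of the table lies inside that, but sampling error shrinks as a group grows and this bias does not. The direction is unknown.

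**Period overlap.** Let a share f of usual-care controls be enrolled after the restart, and assume that care then equals care during the hold. The contrast between usual care and pandemic usual care keeps 1 − f of the true period difference: 100% at f = 0, 75% at 0.25, 50% at 0.5, 25% at 0.75 and none at 1. The number enrolled before the hold is not given, so f is unknown.

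**The case against.** The strongest reply is that much of this is disclosed and little depends on it. The plan calls the cohort retrospective and observational, limits its data to what is recorded, and says care may differ. The comparison is secondary, in a pilot whose stated aim is to estimate effect size. That bears on severity. It does not repair the analysis, which would still compare charted scores with scheduled ones.

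The randomised arms also have gaps. Under section 3b, a patient with no in-person visit scheduled after discharge contributes only the 90-day mRS. This stands: the contrast at 30 days is less sharp than Table 1 alone suggests.

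Several stronger readings are tempting but are not supported:

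- A reader might infer that the plan says mobility care was cut back. It says care was similar and that reprioritisation was possible.
- A reader might infer that no three-group comparison can be made. The 90-day mRS is named in the Aim 2 hypothesis and collected routinely, and delirium and infections come from the record in every group.
- A reader might infer that the whole usual-care arm is pandemic care. Patients randomised before March 16, 2020 are unaffected. For later controls, protective-equipment training shows that they are treated during the pandemic, but not that mobility care was still reduced.
- A reader might infer that the randomised comparison is compromised. Both arms share each period, so it is not, and a period factor there would be a matter of preference.

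**Conclusion.** The point holds in a limited form. For MRC, grip, Barthel and mRS at NCCU discharge and 30 days, following the plan gives a three-group comparison confounded by how, and in whom, the outcome was measured. The Background section's promise of all non-biologic, non-survey variables is not secured by the chart-only collection in section 3a. The two usual-care conditions are also not cleanly separated unless controls are split by enrolment date.

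The size is unknown. The range of 0.03 to 0.70 SD rests on assumed charting shares and assumed differences between charted and uncharted patients. The 1 − f dilution rests on an unknown f and on care after the restart matching care during the hold. This should be corrected, but it concerns a secondary, non-randomised comparison and leaves the two-arm randomised analysis intact.

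**What to change.** In Study Statistics, part c, Aim 2, with matching wording in secondary objective (i) and the Background section:

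1. Limit the three-group comparison to outcomes with a common routine source: 90-day mRS from the stroke service's call, discharge location, delirium positive days and hospital acquired infections. Confirm that discharge location is taken from the record in all groups.
2. Keep MRC, grip, Barthel and the discharge and 30-day mRS for the randomised two-arm comparison only.
3. Report completeness of each outcome by group. This includes the 90-day mRS, since the plan does not say how complete the calls were during the hold.
4. Classify each control as enrolled before the hold or after the restart. Make pre-hold controls versus the pandemic cohort the period contrast, and show post-restart controls separately.
5. Label the three-group comparison exploratory and non-randomised.

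The cost is wording, fewer outcomes in the three-group comparison, and small control subgroups: 20 controls per stroke cohort, divided by date. No new data collection is needed beyond recording the enrolment period.
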